### 8.3. Drug Administration

The DTG-DT will be administered with water and drug administration for neonates will adapted from the package insert instructions (19).

To administer 5 mg of DTG to neonates:

- Break the 10 mg scored DTG-DT in half along the score.
- Mix one half (5 mg) of the DTG-DT for oral suspension in 5 mL (one teaspoonful) of drinking water
- Swirl the suspension so that no lumps remain
- After completely mixed draw up all the prepared medicine into a 5 mL syringe
- Place the tip of the syringe against the inside of the neonate's cheek and give the dose slowly
- Swirl a further 5 mL of drinking water into the dosing cup, draw it into the syringe, and give it all to the neonate. (Do not use any other drink to prepare the dose)
- Give the oral suspension to the child within 30 minutes of mixing

#### **8.4. Direct Observed Treatment**

The study nurse will prepare and administer a single 5 mg dose (half of a 10 mg scored DTG-DT) in Stage 1 (Cohorts 1A and 1B). Direct observation of treatment administration (DOT) will be performed for all neonates at the PK visits in Stage 2. For first administration in Stage 2 (Cohort 2), the investigator will explain drug administration to the caregiver and then observe as the caregiver administer the drug. Observed administration will provide an opportunity for the caregivers to have a first experience with administration of DTG in the presence of the investigator, hence the opportunity to address any difficulties. Prior to Visit 2 in Cohort 2, mothers will be contacted to ensure the DTG doses were administered per dosing schedule.

#### **8.5. Study Treatments Labelling, Packaging and Storage**

This is an open label study. Following study approval from Stellenbosch University (SU) Health Research Ethics Committee (HREC), South African Health Products Regulatory Authority (SAHPRA), and the WHO Ethics Committee, Viatrix Ltd will supply the study drugs under controlled temperature conditions and the labels will follow country requirements (in particular: product name, composition, batch number/Lot No., expiry date and storage instructions).

The drugs will be shipped under controlled temperature to the pharmacy at the FAMCRU site, which is managed by the study pharmacist. After receipt, the pharmacist will verify the drug status for sealed condition of bottles, and the quantities received against the information provided by Viatrix Ltd for the shipped drugs. All study medications must be kept in the pharmacy and access limited only to the appropriate study personnel and stored per recommendations. Storage temperature monitoring records will be maintained by the study pharmacist and kept at the pharmacy.

#### **8.6. Study Drug Accountability**

Study-specific forms will be used for accountability of the study medication. Appropriate records concerning receipt, use, returns, loss and any other disposition of the study medication will be maintained by investigators or their delegates on site, under the supervision of the Principal Investigator. Study monitors will check and document accountability and expiry details of the study medication during on-site monitoring visits.

The investigational medicinal product cannot be used for purposes other than this study. Under no circumstances may the investigator or site staff allow the medications to be used other than as directed by this protocol. Adequate records on receipt, use, return, loss, or other disposition of medication must be maintained.

In Cohort 2, parents will bring back remaining drugs for purposes of pill count and calculation of adherence by site staff. Adherence will be documented in the Case Report Form (CRF).

#### **8.7. Concomitant Treatments**

A complete list of current medications will be taken at the screening/entry visit and at all other visits, including on the day of PK sampling. Any concomitant medications will be evaluated for known interactions with the investigational products and will be checked with the package insert and on the [www.hiv-druginteractions.org](http://www.hiv-druginteractions.org) website to see whether the concomitant treatment may be problematic.

DTG is contraindicated in patients with previous hypersensitivity reaction to dolutegravir. Dofetilide is the only contraindicated medication listed in the DTG package and is not allowed. Potential participants who are receiving medications that require a DTG dose adjustment to twice daily (e.g., rifampicin, phenobarbitone) will be excluded from entry in this study.

Medications containing polyvalent cations, oral iron and/or calcium supplements reduce DTG exposures, and changes to the timing of DTG administration relative to concomitant drugs are necessary to overcome this effect. Any participants receiving such medications will have DTG administered at least 2 hours before or 6 hours after taking the medication/supplements containing polyvalent cations, calcium or iron.

During the study, should there be a clinical indication for any additional medication including medication given to treat an adverse event after study drug(s) administration, the name of the drug(s), the dosage, and the date and time of administration must be recorded on the CRF.

[figure not shown]
## 9. Study Procedures and Assessments

### 9.1. Screening and Enrolment Procedures

Tygerberg Hospital has an active HIV PMTCT service as part of standard of care. The role of this routine PMTCT service is to actively identify, care for and collect real-time information on mothers with HIV (and their neonates) delivering at Tygerberg Hospital. Data generated are submitted to the Department of Health for statistical analysis. The PMTCT nurses ensure that mothers with HIV and their neonates receive the appropriate ARV treatment/prophylaxis, and are linked back to HIV care, if needed. The PETITE-DTG study team will not directly contact potential participants within the routine PMTCT service, rather the medical staff working in the routine PMTCT services will refer potential study participants to the study team for consideration. All mothers referred will first be consulted by medical staff from the routine PMTCT services in order to determine whether they agree to be in contact with the PETITE-DTG research team.

**Figure 2** illustrates the procedure for the initial assessment of study eligibility, i.e., the routine PMTCT services identifying HIV-exposed neonates who meet the Stage and Cohort-specific inclusion criteria. The PMTCT nurses will then inform the study team of a potential participant. Postpartum women with HIV receiving DTG-based ART will be allowed to breastfeed or formula feed depending on the mothers' choice. Documentation of maternal HIV-1 RNA result (performed per standard of care) required as part of the inclusion criteria for neonates in Stage 2 will be abstracted from the medical records. If an HIV-exposed neonate is identified as eligible, the parent(s) will be approached to undergo the informed consent process. Following written informed consent from the parent(s) or legal guardian, the participant will be screened for eligibility. A medical history, clinical examination and study required bloods (haematology, chemistry and HIV NAT samples) will be carried out by the study team. If the study required bloods were taken as part of clinical care, results will be documented, and no additional blood draws performed. If the study required bloods (haematology and chemistry) are abnormal (Section 7.2), the neonate will be referred to routine care. Only if the study required bloods (haematology and chemistry) are within the range specified for eligibility will the neonate be allocated to either Cohort 1A, Cohort 1B or Cohort 2 and follow the SOE for that respective Cohort (Section 9.3). Laboratory tests may be repeated during the screening period, with the latest results used to determine exclusion of participant from study enrolment.

**Figure 2:** Summary of procedure for the initial assessment of study eligibility

## 9.2. Description of Study Procedures and Assessments

### 9.2.1. Stage 1, Cohort 1A: Screening/Entry Visit

The screening and entry visit(s) will take place when the neonate is <14 days of life. Screening and entry procedures may be performed as one or 2 separate visit(s). HIV-exposed neonates enrolled in Cohort 1A will continue to receive ARV prophylaxis as per local guidelines for the duration of the study.

If an HIV NAT test result comes back positive for a neonate at any time during the study, the neonate will come off study and will be treated as per standard of care (any prior PK samples will be included in the analysis).

At the end of study follow-up, HIV negative infants will continue standard of care HIV prophylaxis, if indicated, as per local guidelines.

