
Study design
	
Participants will be enrolled in two stages:
 
 
Stage 1 will assess a single dose of the DTG dispersible tablet in two sequential cohorts: Cohort 1A (n=8) and Cohort 1B (n=8).
 
Stage 2 will assess multiple-doses of the DTG dispersible tablet in a single cohort: Cohort 2 (n=24).
 
 
Per national guidelines, all infants receive a birth HIV nucleic acid test (NAT). HIV NAT test results for the infant may or may not be available (HIV pending) at the time of study entry. If an HIV NAT result comes back positive whilst the neonate is on study, the neonate will not receive any further DTG doses, revert to standard of care antiretroviral therapy (ART), and be followed for safety for the duration of the study.
 
Stage 1: Single Dose of the DTG dispersible tablet
 
Eligible HIV-exposed term neonates (pending HIV status) on standard of care ARV prophylaxis will be enrolled. Cohort 1A will open first.
 
 
Cohort 1A: 8 neonates weighing <math>\geq 2000</math> g at birth, born to women on DTG-based ART, will receive a single 5 mg dose of the DTG dispersible tablet at <math>\geq 14</math> days and <math>< 28</math> days of life. Following DTG administration, blood samples (0.4 mL/time point) will be drawn at 1, 2, 3, 4, 6, 24-30 hours post-dose. All neonates will be followed for safety until 2 weeks after the pharmacokinetic evaluation visit. DTG will be administered in addition to standard of care ARV prophylaxis.
 
 
After Cohort 1A is complete, and if no safety concerns are noted, accrual will continue into Cohort 1B. However, if safety hold criteria are met in Cohort 1A (Section 11.1.1), the study will be paused and data reviewed by the Data and Safety Monitoring Board (DSMB).
 
 
Cohort 1B: 8 neonates weighing <math>\geq 2000</math> g at birth, born to women on DTG-based ART, will receive a single 5 mg dose of the DTG dispersible tablet at <math>< 14</math> days of life. Following DTG administration, blood samples (0.4 mL/time point) will be drawn pre-dose, and at 1, 2, 4, 6, and 24-72 hours post-dose. All neonates will be followed for safety until 2 weeks after the PK visit. DTG will be administered in addition to standard of care ARV prophylaxis.
 

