### 5.3. Endpoints

#### 5.3.1. Primary endpoints

- DTG plasma pharmacokinetics parameters: area under the concentration time curve (AUC); maximum plasma concentration ( $C_{max}$ ), apparent clearance (CL/F), and trough concentration ( $C_{trough}$ )
- Occurrence of the following events: adverse events of Grade 3 or higher; treatment-related adverse events of Grade 3 or higher; any adverse events

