### 9.2.2. Stage 1: Cohort 1B

The screening and entry visit(s) will take place within ≤3 days of life. Screening and entry procedures may be performed as one or 2 separate visit(s). HIV-exposed neonates enrolled in Cohort 1B will continue to receive ARV prophylaxis as per local guidelines for the duration of the study.

If an HIV NAT test result comes back positive for a neonate at any time during the study, the neonate will not receive any further study drugs, come off study and will be treated as per standard of care (any prior PK samples will be included in the analysis).

At the end of study follow-up, HIV negative infants will continue standard of care HIV prophylaxis, if indicated, as per local guidelines.

### 9.2.2.1. Cohort 1B: PK Visit 1

After study entry, PK visit 1a and 1b for the neonate will be scheduled at **< 14 days of life**. On the morning of the PK visit, study nurses and physicians will take a medical history and examine the neonate. Afterwards, a single 5 mg dose of DTG (half of the 10 mg DTG-DT) will be administered. The study team will support the preparation and administration of the DTG-DT mixed with water with the mother and document the exact time of intake used for administration. Acceptability testing of the DTG-DT will be performed.

Blood will be drawn pre-dose, and then following an observed dose, at 1, 2, 4, and 6 (PK Visit 1a), and 24-72 hours (PK Visit 1b) post-dose. A blood draw window of +/- 15 minutes is acceptable for samples up to 6 hours post-dose. The last sample can be drawn anytime between 24 and 72-hours post-dose. It is planned to draw 0.4 mL per time point - a total blood volume of 2.4 mL for PK assessment. A short intravenous catheter (heparin lock) can be used to reduce repeated skin puncture and ease the discomfort of blood sampling.

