### 9.2.3.1. Cohort 2: Screening and Entry visit(s)

The screening and entry visit(s) will take place when the neonate is <7 days of life (Section 9.1). Screening and entry procedures may be performed as one or 2 separate visit(s). At the Entry visit, ZDV prophylaxis will be initiated instead of NVP and continue until DTG is stopped at Day 28 of life. Thereafter, the infant will switch back to NVP from ZDV and continue prophylaxis per national guidelines.

The study team will support the preparation and administration of the 1st dose of the DTG-DT (half-tablet) mixed with water with the parent(s) or caregiver/legal guardian. The exact time of intake will be recorded. The mother will be explained how to prepare and administer DTG at home. Acceptability testing of the DTG-DT will be performed.

Two blood samples will be drawn for PK assessment, one sample immediately prior to administering the 1st DTG dose and another sample at 1-3 hrs post-dose (**Table 5**). It is planned to draw 0.4 mL of blood per time point.

### 9.2.3.2. Cohort 2: Study Visits 2 and Visit 3

It is anticipated that DTG could be dosed every 24, every 48 or every 72 hours, or some other combination, that is expected to achieve target DTG concentrations throughout the first 4 weeks of life. The PK sampling schedule has been designed to cover these different possible dosing scenarios.

After the Entry, Visit 2 can be scheduled at **any time from the 3rd dose of DTG** but before Week 4 of life. The mother will be instructed not to administer the morning DTG dose prior to attending this study visit. On the morning of Visit 2, clinic study nurses and physicians will take a medical history, examine the neonate, and assess adherence. Assessments will include dispensing diary cards to caregivers, reviewing or collecting diary cards and establishing study drug adherence (pill count). The PK assessment should be deferred if the mother/caregiver reports their baby missing any of the previous 3 scheduled doses prior to the PK sampling visit (Section 9.4).

Prior to the morning DTG dose, a blood sample will be taken for pre-dose PK evaluation and then the protocol-specified DTG dose will be administered. The exact time of intake will be recorded. Acceptability testing of the DTG-DT will be performed.

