### 9.3. Schedule of Evaluations

**Table 6.** Schedule of evaluations for Stage 1 Cohort 1A (n=8): Single dose of DTG in neonates in week 3 and 4 of life

Evaluation	Screening and Entry Visit(s) a	PK Visit 1a	PK Visit 1b	Safety Visit 1	Safety Phone Call
Visit windows	< 14 days of life	≥ 14 days and less than 28 days of life	24-30 hours post single DTG dose	1 week after PK Visit 1a (+/-4 days)	2 weeks after PK Visit 1a (+/-4 days)
Clinical					
Informed Consent	X				
History	X	X	X	X	X
Physical examination b	X	X		X	
Dispense DTG		X			
Acceptability questionnaire		X			
Laboratory					
Haematology c	X (0.5 mL)			X (0.5 mL)	
Chemistry d	X (0.8 mL)			X (0.8 mL)	
HIV-1 NAT Test e	X (0.8 mL)			X (0.8 mL)	
Pharmacology					
PK Blood Sampling f		X (2mL)	X (0.4mL)		
Total blood volume	2.1 mL	2 mL	0.4 mL	2.1 mL	

a Screening and entry procedures may be performed as one or 2 separate visit(s). All study required results should be available before entry with the exception of the HIV-1 NAT result which may be pending at time of study entry; b Physical and medical assessment includes length, weight, head measurements and monitoring of vital signs; c Haemoglobin, white blood cell count and differential, and platelets; d Creatinine, ALT, AST, total and direct bilirubin; e If HIV-1 NAT Test comes back positive, the HIV-infected neonate will be taken off study and initiated on standard of care HIV-treatment, as per local guidelines; f PK blood sampling at PK Visit 1a/b will occur at 1, 2, 3, 4, 6 and 24-30 hours post DTG single dose. Mothers and their neonates will return home after PK Visit 1a sampling time-points (1, 2, 3, 4 and 6 hours) and attend the following day for PK Visit 1b to complete the 24-30 hour PK sampling procedure. Laboratory tests may be repeated during the screening period dependent on specified blood draw limits.

**Table 7.** Schedule of evaluations for Stage 1 Cohort 1B (n=8): Single dose of DTG in neonates in week 1 and 2 of life

Evaluation	Screening and Entry Visit(s) a	PK Visit 1a	PK Visit 1b	Safety Visit 1	Safety Phone Call
Visit windows	≤3 days of life	<14 days of life	24-72 hours post single DTG dose	1 week after PK Visit 1a (+/-4 days)	2 weeks after PK Visit 1a (+/-4 days)
Clinical					
Informed Consent	X				
History	X	X	X	X	X

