Total blood volume	2.9 mL	2.8 mL	0.4 mL	1.3 mL	2.4 mL	

a Screening and entry procedures may be performed as one or 2 separate visit(s). All study required results should be available before entry with the exception of the HIV-1 NAT result which may be pending at time of study entry; b Visit 2 and 3 should be scheduled any time from 3rd DTG dose but before week 4 of life; c Visit 4 can be conducted on the same day as Visit 5 but only if both falls within week 4 of life; d Physical and medical assessment includes length, weight, head measurements and monitoring of vital signs vital signs; e 1st DTG dose administered <7 days. The timing of the next dose of DTG and subsequent DTG doses will be determined using data from Cohort 1A and 1B. DTG will be administered until the neonate is 28 days old; f Haemoglobin, white blood cell count and differential, and platelets; g Creatinine, ALT, AST, total and direct bilirubin; h If HIV-1 NAT Test comes back positive, the HIV-infected neonate will be taken off study and initiated on standard of care HIV-treatment, as per local guidelines; i For the 1st DTG dose (PK: pre-dose sample and 1 more sample 1-3 hours post-dose); Any time from 3rd DTG dose but before week 4 of life (PK: pre-dose and 1, 2, 4, 6 and 24-72 hours post dose); For any DTG dose in Week 4 of life (PK: pre-dose sample and another sample 1-3 hours post-dose). Laboratory tests **may not** be repeated during the screening period as this will exceed blood draw limits.

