### Analysis Populations

The following analysis populations will be used in this study:

- Screened: all infants who were screened for eligibility.
- Enrolled: all infants who passed screening and entered the study.
- Safety: all enrolled infants who received at least one dose of study treatment.
- PK: all infants in the Safety population who had at least one PK assessment.

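### The protocol gives two incompatible rules for an infant whose HIV test turns positive on study: continued safety follow-up, or removal from the study

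*Protocol*

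**What the plan says.** The synopsis states the first rule for all cohorts. After a positive NAT the infant receives no more DTG, reverts to standard antiretroviral therapy, "and be followed for safety for the duration of the study". Sections 6.1 and 13.6 repeat it.

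Section 9 states the second rule, cohort by cohort. For Cohort 1A (9.2.1), "the neonate will come off study and will be treated as per standard of care". For Cohort 1B (9.2.2), and in the same words for Cohort 2 (9.2.3), "the neonate will not receive any further study drugs, come off study and will be treated as per standard of care". The footnotes to Tables 6, 7 and 8 in 9.3 say that "the HIV-infected neonate will be taken off study and initiated on standard of care HIV-treatment".

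Three other provisions decide whether this matters:
- All screening results must be in hand before entry, "with the exception of the HIV-1 NAT result which may be pending at time of study entry". In Cohort 2 the first DTG dose is given at the Entry visit (9.2.3.1).
- The primary safety endpoint in 5.3.1 includes "treatment-related adverse events of Grade 3 or higher; any adverse events".
- The Safety population is "all enrolled infants who received at least one dose of study treatment", with no exception for a positive NAT.

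**The concern.** The same event leads to different visits depending on the page the site reads. Section 9 and its tables direct the visits, while 13.6, the benefit-risk section, says that safety follow-up continues.

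If staff follow Section 9, an infant who has received an investigational drug stays in the denominator of the primary safety analysis after scheduled ascertainment has ended. Events that start after removal may go unrecorded. Drug exposure also outlasts the last dose: 8.2.1 reports a median washout half-life of 32.8 hours in neonates exposed in utero. A later statistical analysis plan cannot repair this, because it does not decide which visits are made.

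**Working it through.** **1. The two rules side by side**

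| Place | Stop DTG | Standard treatment | Follow-up |
|---|---|---|---|
| Synopsis, 6.1, 13.6 | stated | stated | safety follow-up to study end |
| 9.2.1 (1A) | not stated separately | stated | off study |
| 9.2.2 (1B), 9.2.3 (2) | stated | stated | off study |
| Footnotes, Tables 6–8 | not stated separately | stated | off study |
| 10.8 | stated | silent | silent |

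Off study might be meant as off drug. In 9.2.2 and 9.2.3 it cannot be, because both steps are listed. In 9.2.1 and the footnotes that reading is not excluded by the wording alone. The synopsis rule carries no cohort limit, so the two rules cannot be assigned to different cohorts.

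**2. What one infant loses under the Section 9 rule**

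- *Cohort 2, stopped before Visit 2.* Visit 2 opens from the third dose and Visit 4 is timed from Visit 2. NAT results typically arrive within 72 hours (6.1). The third dose falls two intervals after the first: 48, 96 or 144 hours with 24-, 48- or 72-hour dosing. An infant stopped early may therefore have no date for Visits 2 and 4 even under the follow-up rule. The contacts with a fixed date are Visit 5 (Day 22–28, with chemistry) and the call two weeks later.
- *Cohort 2, first positive at Visit 5.* Only the call is lost.
- *Cohort 1B, dosed with the NAT pending.* Entry is at 3 days of life or earlier, and the dosing window (under 14 days) has no stated minimum, although 8.2.1 describes a dose after day 3. Such an infant would lose Safety Visit 1, the only post-dose laboratory check, and the call.
- *Cohort 1A.* The dose is at 14 days or later and entry is earlier, so the entry NAT is normally known before dosing. A positive at Safety Visit 1 costs the call.

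**3. How many infants**

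Inputs: n = 24 (12.1) and p = 0.7%, the national rate over the first two months of life (6.3). The lower rates are assumptions. Expected number = n × p; chance of at least one = 1 − (1 − p)^n.

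| p | Expected, Cohort 2 | Chance of at least one |
|---|---|---|
| 0.7% | 24 × 0.007 = 0.168 | 1 − 0.993^24 = 0.155 |
| 0.35% (assumed) | 24 × 0.0035 = 0.084 | 1 − 0.9965^24 = 0.081 |
| 0.1% (assumed) | 24 × 0.001 = 0.024 | 1 − 0.999^24 = 0.024 |

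For all 40 infants at 0.7% the figures are 0.28 and 0.245. The same formula reproduces Table 10 (1% with N = 24 gives 0.21; 5% with N = 40 gives 0.87).

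The 0.7% is a ceiling for Cohort 2. Mothers there have fewer than 50 copies/mL, infants known to be infected are excluded at entry (7.2), the rate runs to two months, and it includes infants first positive at Visit 5.

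**4. Where the follow-up time lies**

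Assume equal risk per NAT and the following weeks lost, estimated from the visit schedule: Cohort 2 entry NAT 4–5, Visit 5 NAT 2; Safety Visit 1 NAT in Stage 1, 1; Cohort 1B entry NAT 0–2; Cohort 1A entry NAT 0.

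- Cohort 2: 24 × (4 + 2) = 144 to 24 × (5 + 2) = 168
- Stage 1: 16 × 1 + 8 × 0 = 16 to 16 × 1 + 8 × 2 = 32
- Cohort 2 share: 144/176 = 82% to 168/184 = 91%

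Cohort 2 keeps more than half of this time unless its risk is below about 0.10 (16/168) to 0.22 (32/144) of the Stage 1 risk. It holds more than half of the expected positives only if its risk exceeds 16/24 = 0.67 of the Stage 1 risk.

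**5. Effect on the endpoint**

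One infant whose only event is missed lowers a Cohort 2 proportion by 1/24 = 4.2 percentage points. For scale, the 95% Clopper-Pearson interval is 0 to 14.2% for 0/24 and 0.1% to 21.1% for 1/24.

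**The case against.** The strongest reply is that no version continues DTG: each stops it or moves the infant to standard treatment, so the infant's immediate protection is not in dispute. Recorded events are kept. Every Grade 3 or higher event is a serious event (10.2) and is followed to resolution or a stable state (10.3), and unresolved related events are followed under 13.13. Events after the switch would also be partly confounded with the new drugs. Most likely no infant is affected. All of this stands and limits the size. These safeguards follow events already known, however; they do not schedule detection of new ones.

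A reader might infer that a Cohort 2 infant found positive early loses every post-baseline laboratory check because of this contradiction. The text does not support that, because Visits 2 and 4 may have no date under either rule.

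A reader might also infer that the positive infants will arise mainly in Cohort 2. The documents do not show this. Stage 1 requires no maternal viral load (13.6), whereas Cohort 2 mothers are suppressed, and no transmission rate is given for suppressed mothers. Only the weaker statement, that most of the follow-up time at stake is probably in Cohort 2, has support.

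**Conclusion.** The contradiction is real and should be corrected. It concerns safety follow-up after a positive NAT and nothing else. In 9.2.2 and 9.2.3 no reading reconciles it with the synopsis, 6.1 and 13.6.

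Its size is small. In Cohort 2 at most 0.17 affected infants are expected, with a 16% chance of at least one, if the national rate is accepted as a ceiling. At an assumed 0.1% these fall to 0.02 and 2%. Bias in the endpoint further requires a first event after removal that goes unreported. The statement about follow-up time rests on approximate weeks and equal risk per test.

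A reader might go further and conclude that the primary safety analysis or the safety-hold rules are compromised. The documents do not support that: sample size, analysis populations and decision rules are unaffected. The synopsis rule is the better one to keep, because it matches the protocol elsewhere. Infants stay in safety follow-up when Stage 1 PK sampling is terminated (9.4) and after permanent discontinuation for a related event (10.8).

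**What to change.** Amend 9.2.1, 9.2.2, 9.2.3 and the NAT footnotes to Tables 6, 7 and 8 to the synopsis rule: a positive NAT stops DTG and PK sampling, starts standard antiretroviral therapy, and the infant stays in safety follow-up.

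For Cohort 2 infants stopped before Visit 2, have the safety checks done at intervals set by the investigator, as 10.8 already allows after discontinuation for a related event. Keep Visit 5 and the call.

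The cost is wording in three subsections and three footnotes, one added sentence for Cohort 2, and a few contacts for a rare infant. On blood, if checks equal to those of Visits 2, 4 and 5 were drawn without PK or NAT samples, the later volume would be 0.8 + 1.3 + 0.8 = 2.9 mL. With 2.9 mL at Entry the total is 5.8 mL, against 9.8 mL for the full Table 8 schedule. That leaves 4.2 mL under the 10 mL 30-day limit for a 2 kg neonate. The limit in 13.7 also covers clinical draws, whose volume for a newly diagnosed infant is not given, so the sentence should require that they be counted.
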